### **Listing/ summary of DLTs**

DLTs will be listed and their incidence summarized by primary system organ class, preferred term and by treatment group. The dose-determining set will be used for these summaries.

#### **10.5.2.2 Phase II**

A simple Bayesian design will be used in order to estimate the ORR and to provide inferential summaries (e.g., mean, median, standard deviation, 95% credible intervals, and interval probabilities) based on the posterior distribution of ORR in the Phase II part. Minimally informative unimodal Beta distributions ([Neuenschwander et al 2008](#)) will be used as prior distribution for the different study groups. These prior distributions reflect the current uncertainty about the efficacy of capmatinib in combination with nazartinib. For the primary analysis the posterior distributions of the ORR will be computed using the available data.

The primary analysis will be performed using the FAS when all participants enrolled in each of the Groups 1 to 4 have completed at least 6 cycles of treatment or discontinued prior to that time for any reason.

Group 3 (EGFRmut, T790M negative, any MET, 1L antineoplastic) will have one interim analysis for futility when approximately 20 participants have completed at least 4 cycles of treatment or discontinued treatment prior to that time.

#### **Group 1 (EGFRmut, any T790M, any MET, 2/4L antineoplastic, EGFR TKI resistant)**

For participants harboring the T790M mutation and participants not harboring the T790M mutation the posterior distribution of the ORR will be computed using the available data at the time of the primary analysis. A minimally informative beta distribution with parameters

$a = 0.1765$  and  $b = 1$  based on a conservative assumption about the mean response rate will be used.

Summaries (e.g., mean, median, standard deviation, 95% credible intervals, and interval probabilities) for the posterior distribution of the ORR will be provided for the T790M+ and T790M- subgroup.

#### **Group 2 (EGFRmut, de novo T790M, any MET, 1/3L antineoplastic, EGFR TKI naïve)**

This group will only be analyzed descriptively due to the expected maximum number of 5 participants enrolled.

#### **Group 3 (EGFRmut, T790M negative, any MET, 1L antineoplastic)**

The ORR will be classified according to the following intervals:

- [0, 40%) unacceptable anti-tumor activity
- [40%, 55%) limited anti-tumor activity
- [55%, 70%) moderate anti-tumor activity
- [70%, 100%] strong anti-tumor activity

An observed ORR  $\geq 55\%$  based on Investigators' assessments will be considered clinically meaningful in this group.

The preliminary anti-tumor activity of the study treatment will be declared if the following two conditions are both fulfilled:

- The posterior median ORR is equal to or greater than 55%
- The posterior risk of being in the unacceptable anti-tumor activity interval is lower than 5%

This will require observing at least 22 responses in 40 participants. Otherwise, the inferential summaries for the 4 intervals above will be assessed for further characterization of the anti-tumor activity. A minimally informative beta distribution with parameters  $a = 1$  and  $b = (1 - 0.55)/0.55 = 0.818$  based on an assumed mean response rate of 0.55 will be used as prior distribution for the Bayesian estimation of the ORR.

An interim analysis for futility will be performed when approximately 20 participants have completed at least 4 cycles of treatment or discontinued treatment prior to that time. More details on the interim analysis are presented in nazartinib.

#### **Group 4 (EGFRmut, any T790M, any MET, 1L (treatment naïve) 2-3L antineoplastic)**

Frequencies of adverse events will be analyzed descriptively in this group as described in Section 10.6.1.2.

### **10.5.3 Handling of missing values/censoring/discontinuations**

**Incidence of DLTs in Cycle 1:** If a Phase Ib participant is considered as non-evaluable for the DDS, enrollment of a new participant to the current cohort will be considered if there is less than the required number of evaluable participants ([Section 6.2.3](#)).

**Overall response rate:** Participants who have missing BOR will be considered as a treatment failure for the primary analysis of ORR.

Participants who have disease progression and continue to receive study drug after progression will qualify for PD at the time of progression and will be counted as PD in the derivation of efficacy endpoints.

#### 10.5.4 Supportive analyses

For the Phase II part the Bayesian analysis of ORR for each Group will be repeated using the PPS, if the PPS is different from the FAS.

### 10.6 Primary objective for Phase II Group 5

Approximately 30 participants will be enrolled in Group 5.

Group 5 will have one interim analysis for futility when 10 participants have completed at least 2 tumor assessments while on treatment with capmatinib monotherapy, had radiological disease progression per RECIST 1.1, or discontinued study treatment prior to that time. Details on the interim analysis are presented in [Section 10.8](#).

#### 10.6.1 Primary estimand

The primary scientific question of interest is to estimate the treatment effect of capmatinib monotherapy based on ORR for the target population regardless of discontinuation of treatment and any unforeseen events resulting from a public health emergency.

Targeting this treatment effect is regarded as a measure for the contribution of capmatinib monotherapy in this population setting within a novel drug combination (capmatinib + third generation EGFR TKI Inhibitor). It is indicated that the median time to response for capmatinib is approximately 6 weeks ([Wolf et al 2020](#)). Moreover, a capmatinib monotherapy period will allow a thorough toxicity washout of the previous TKI. It is reported that a medium washout period for switching of TKIs of 1.1 months ([Sakata et al. 2020](#)).

The primary estimand is characterized by the following attributes:

1. Population: adult NSCLC participants with previously documented EGFR activating mutation (e.g., L858R and/or ex19del), T790M negative, MET amplified (confirmed by central testing), who have progressed on one prior line of therapy (either to first/second generation EGFR TKIs, osimertinib or other third generation EGFR TKIs) for advanced/metastatic disease NSCLC. Further details on the population are provided in [Section 5](#).
2. Treatment: capmatinib monotherapy at a dose of 400 mg b.i.d. (tablets for oral use). Further details about the treatment are provided in [Section 6.1](#).
3. Variable: BOR defined as the best response recorded from the date of treatment start until radiological disease progression/recurrence (taking as reference for disease progression the smallest measurements recorded since the treatment started) based on investigator assessment per RECIST 1.1 with responses after switching to capmatinib plus nazartinib

combination treatment and responses after the use of new (non-study treatment) anti-cancer therapy considered as non-response.

4. Intercurrent events:

- Switching to capmatinib plus nazartinib combination treatment: BOR assessments after switching will be considered as nonresponses and have been accounted for in the variable attribute using the composite strategy
- Start of new anti-cancer therapy: BOR assessments after the use of new anti-cancer therapy will be considered as nonresponses and have been accounted for in the variable attribute using the composite strategy
- Discontinuation of study treatment for any reason (other than starting combination treatment or new anti-cancer therapy): BOR will take into account all response assessments irrespective of the reasons for discontinuing capmatinib monotherapy (treatment policy strategy)
- Any unforeseen intercurrent events (e.g., related to a public health emergency) will be handled by the treatment policy strategy

5. Summary measure: ORR defined as the proportion of participants with confirmed BOR of CR or PR based on investigator assessment per RECIST 1.1

### 10.6.2 Statistical model, hypothesis, and method of analysis

The analysis of the primary endpoint will be performed for participants in the EAS who were treated with capmatinib monotherapy and based on the time period of monotherapy treatment. ORR is defined as the proportion of participants with confirmed best overall response of CR or PR, and will be assessed by the investigator according to RECIST 1.1.

The analysis of Group 5 data will be performed when all participants enrolled in the group have completed at least 6 treatment cycles (about 6 months) or discontinued prior to that time for any reason, provided the Group 5 continued into Stage 2.

The primary efficacy endpoint ORR will be estimated and the 2-sided exact 95% CI (Clopper and Pearson 1934) provided. Capmatinib monotherapy treatment will be considered to have clinically relevant efficacy if the following criteria are fulfilled:

- the ORR estimate is > 45% and
- the lower bound of the two-sided 95% exact CI is >35%.

Based on historical data (Soria et al 2015, Mok et al 2017), the ORR in this population is expected to be around 35% and the threshold of 45% is considered of clinical interest.

### 10.6.3 Handling of intercurrent events of the primary estimand

The intercurrent events for the primary estimand are described in [Section 10.5.1](#).

### 10.6.4 Handling of missing values not related to intercurrent events

Participants without a baseline tumor assessment will not be included in the EAS.

## **10.7 Secondary objectives**

### **10.7.1 Safety objectives**

#### **10.7.1.1 Analysis set and grouping for the analyses**

For all safety analyses, the safety set will be used if not otherwise specified. All listings and tables will be presented by treatment group.

#### **Phase Ib and Phase II Group 1 to Group 4**

The overall observation period will be divided into three mutually exclusive segments:

- pre-treatment period: from day of participant's informed consent to the day before first dose of study medication
- on-treatment period: from day of first dose of study medication to 30 days after last dose of study medication
- post-treatment period: starting at day 31 after last dose of study medication.

#### **Phase II Group 5**

For the safety analysis of capmatinib monotherapy in Group 5, the overall observation period will be divided into the following three mutually exclusive segments:

- pre-treatment period: from day of participant's informed consent to the day before first dose of study medication
- on-treatment period:
  - from day of first dose of study medication to 30 days after last dose of capmatinib monotherapy, if the participant did not continue on combination therapy, or
  - from day of first dose of study medication to the data prior to the start of capmatinib plus nazartinib combination therapy, if the participant continued on combination therapy
- post-treatment period:
  - starting at day 31 after last dose of study medication, i.e., capmatinib monotherapy, if the participant did not continue on combination therapy, or
  - starting at day 31 after last dose of combination therapy, if the participant received combination therapy.

For the safety analysis of capmatinib plus nazartinib combination therapy 5, the overall observation period will be divided into the following three mutually exclusive segments:

- pre-treatment period: from day of participant's informed consent to the day before the first dose of combination therapy
- on-treatment period: from day of first dose of combination therapy to 30 days after last dose of study medication
- post-treatment period: starting at day 31 after last dose of study medication.

### 10.7.1.2 Adverse events (AEs)

Summary tables for AEs have to include only AEs that started or worsened during the on-treatment period, the *treatment-emergent* AEs. However, all safety data (including those from the pre and post-treatment periods) will be listed and those collected during the pre-treatment and post-treatment period are to be flagged. Listings of all AEs will be provided based on the FAS.

The incidence of treatment-emergent adverse events (new or worsening from baseline) will be summarized by system organ class or preferred term, severity (based on CTCAE grades), relationship to study treatment and by treatment group.

Deaths reportable as SAEs and non-fatal serious adverse events will be listed by participant and tabulated by type of adverse event and treatment group.

Serious adverse events, non-serious adverse events and adverse events of special interest (AESI) during the on-treatment period will be tabulated.

### 10.7.1.3 Laboratory abnormalities

For laboratory tests covered by the CTCAE version 4.03 for participants in Phase Ib and Phase II (Groups 1 to 4) and version 5.0 for participants in Phase II Group 5, the study's biostatistical and reporting team will grade laboratory data accordingly. The calculation of CTCAE grades will be based on the observed laboratory values only, clinical assessments will not be taken into account. For laboratory tests covered by CTCAE, a Grade 0 will be assigned for all non-missing values not graded as 1 or higher. Grade 5 will not be used.

For laboratory tests where grades are not defined by CTCAE, results will be graded by the low/normal/high classifications based on laboratory normal ranges.

The following by-treatment summaries will be generated separately for hematology, biochemistry and urinary laboratory tests:

- frequency table for newly occurring on-treatment grades 3 or 4 (see below for details)
- shift tables using CTCAE grades to compare baseline to the worst on-treatment value
- for laboratory tests where CTCAE grades are not defined, shift tables using the low/normal/high/(low and high) classification to compare baseline to the worst on-treatment value.
- listing of all laboratory data with values flagged to show the corresponding CTCAE grades and the classifications relative to the laboratory normal ranges.

### 10.7.1.4 Other safety data

#### ECG

- shift table baseline to worst on-treatment result for overall assessments
- listing of ECG evaluations for all participants with at least one abnormality.

#### Vital signs

- shift table baseline to worst on-treatment result

- table with descriptive statistics at baseline, one or several post-baseline time points and change from baseline to this/these post-baseline time points.

#### **10.7.1.5 Tolerability**

Tolerability of study drugs will be assessed by summarizing the frequency of dose interruption, frequency of dose reduction, and dose intensity. Reasons for dose interruption and dose reduction will be listed by participant and summarized.

#### **10.7.2 Efficacy objectives**

CT/MRI assessments will be used for all efficacy assessments of anti-tumor activity on study. BOR, ORR, PFS, DCR, duration of response (DOR) and Time To Response (TTR) will be defined as per RECIST 1.1 (see [Section 14.1](#)) based on investigator assessment. The analyses will be based on the FAS for groups 1 to 4 and the EAS for Group 5. Summaries by group will be based on baseline mutation status and prior systemic antineoplastic therapies as specified in the eCRF. Listings of efficacy endpoints will be presented by treatment group.

If available, the results of the central evaluations by BIRC may be used for secondary analyses purposes.

##### **10.7.2.1 Secondary efficacy endpoints for Phase Ib and Phase II Groups 1 to 4**

**Phase Ib part:** Overall response rate (ORR), duration of response (DOR), disease control rate (DCR), time to response (TTR), and progression-free survival (PFS) by Investigator assessment in accordance with RECIST 1.1 and overall survival (OS).

**Phase II part:** DOR, DCR, TTR, PFS by Investigator assessment in accordance with RECIST 1.1, and overall survival (OS). In addition for Group 4 ORR by investigator assessment in accordance with RECIST 1.1.

#### **Best overall response**

BOR is the best response recorded from the start of the treatment until documented radiological disease progression/recurrence. However, any assessments taken more than 28 days after the last dose of study treatment will not be included in the best overall response derivation.

The study requires that for a partial response (PR) or complete response (CR) changes in tumor measurements must be confirmed by repeat assessments performed not less than 4 weeks after the criteria for the response are first met.

BOR will be summarized by treatment group.

#### **Overall response rate**

ORR is defined as the proportion of participants with a best overall confirmed CR or PR per RECIST 1.1.

ORR will be estimated together with the exact binomial 95% confidence interval (CI) ([Clopper and Pearson 1934](#)).

### **Duration of response**

Among participants with a confirmed PR or CR per RECIST 1.1, DOR is defined as the time from first documented response (PR or CR) to the date of first documented disease progression or death due to underlying cancer. If a participant did not have an event or received any further anticancer therapy before documented disease progression, DOR is censored at the time of the last adequate tumor assessment.

DOR will be described using the Kaplan-Meier method including the estimated median (in months) with 95% CI, as well as the 25th and 75th percentiles. For the Phase Ib part the summary will be provided only in treatment groups with sufficient numbers of participants. Summary statistics of DOR for participants whose best response is CR or PR will be provided for groups with  $\leq 5$  responders. For the Phase II part a Kaplan Meier plot will also be presented.

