### **Progression-free survival**

PFS is defined as the time from the date of first dose of study treatment to the date of first documented disease progression per RECIST 1.1 or death due to any cause. If a participant did not have an event or received any further anticancer therapy before documented disease progression, PFS will be censored at the time of the last adequate tumor assessment. By default, if disease progression or death is documented after one single missing tumor evaluation, the actual event date of disease progression/death will be used for the PFS event date. If disease progression or death is documented after two or more missing tumor evaluations, the PFS time of these participants will be censored at the date of the last adequate tumor assessment without PD. Clinical deterioration without objective radiological evidence will not be considered as documented disease progression.

PFS will be described using the Kaplan-Meier method including the estimated median (in months) with 95% CI, 25th and 75th percentiles. For the Phase Ib part the summary will be

provided only in treatment groups with sufficient numbers of participants. For the Phase II part a Kaplan Meier plot will also be presented. In addition, the PFS rates and 95% confidence intervals at 6, 12, 18 and 24 months will be estimated.

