#### **10.7.2.2 Secondary efficacy endpoints for Phase II Group 5**

DOR, DCR, and PFS for capmatinib monotherapy will be analyzed as secondary efficacy endpoints for Group 5.

The analyses will be based on the EAS. The endpoint definition follows the description in Section 10.6.2.1.

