#### 14.1.3.2.3 Time to progression

Some studies might consider only death related to underlying cancer as an event which indicates progression. In this case the variable “Time to progression” might be used. TTP is defined as PFS except for death unrelated to underlying cancer.

**Time to progression (TTP)** is the time from date of randomization/start of treatment to the date of event defined as the first documented progression or death due to underlying cancer. If a patient has not had an event, time to progression is censored at the date of last adequate tumor assessment.

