#### 14.1.3.2.6 Duration of response

The analysis of the following variables should be performed with much caution when restricted to responders since treatment bias could have been introduced. There have been reports where a treatment with a significantly higher response rate had a significantly shorter duration of response but where this probably primarily reflected selection bias which is explained as follows: It is postulated that there are two groups of patients: a good risk group and a poor risk group. Good risk patients tend to get into response readily (and relatively quickly) and tend to remain in response after they have a response. Poor risk patients tend to be difficult to achieve a response, may have a longer time to respond, and tend to relapse quickly when they do respond. Potent agents induce a response in both good risk and poor risk patients. Less potent agents induce a response mainly in good risk patients only. This is described in more detail by [Morgan \(1988\)](#).

It is recommended that an analysis of all patients (both responders and non-responders) be performed whether or not a “responders only” descriptive analysis is presented. An analysis of responders should only be performed to provide descriptive statistics and even then interpreted with caution by evaluating the results in the context of the observed response rates. If an inferential comparison between treatments is required this should only be performed on all patients (i.e. not restricting to “responders” only) using appropriate statistical methods such as the techniques described in [Ellis et al \(2008\)](#). It should also be stated in the protocol if duration of response is to be calculated in addition for unconfirmed response.

For summary statistics on “responders” only the following definitions are appropriate. (Specific definitions for an all-patient analysis of these endpoints are not appropriate since the status of patients throughout the study is usually taken into account in the analysis).

**Duration of overall response (CR or PR):** For patients with a CR or PR (which may have to be confirmed the start date is the date of first documented response (CR or PR) and the end date and censoring is defined the same as that for time to progression.

The following two durations might be calculated in addition for a large Phase III study in which a reasonable number of responders is seen.

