**Table 14-5 Options for event dates used in PFS, TTP, duration of response**

Situation		Options for end-date (progression or censoring)  (1) = default unless specified differently in the protocol or RAP	Outcome
A	No baseline assessment	(1) Date of randomization/start of treatment 	Censored
B	Progression at or before next scheduled assessment	(1) Date of progression (2) Date of next scheduled assessment 	Progressed Progressed
C1	Progression or death after exactly one missing assessment	(1) Date of progression (or death) (2) Date of next scheduled assessment 	Progressed Progressed
C2	Progression or death after two or more missing assessments	(1) Date of last adequate assessment  (2) Date of next scheduled assessment  (3) Date of progression (or death)	Censored Progressed Progressed
D	No progression	(1) Date of last adequate assessment	Censored
E	Treatment discontinuation due to 'Disease progression' without documented progression, i.e. clinical progression based on investigator claim	(1) Ignore clinical progression and follow situations above (2) Date of discontinuation (visit date at which clinical progression was determined)	As per above situations Progressed
F	New anticancer therapy given	(1) Ignore the new anticancer therapy and follow situations above (IIT approach) (2) Date of last adequate assessment prior to new anticancer therapy (3) Date of secondary anti-cancer therapy (4) Date of secondary anti-cancer therapy	As per above situations Censored Censored Event
G	Deaths due to reason other than deterioration of 'Study indication'	(1) Date of last adequate assessment	Censored (only TTP and duration of response)

. =Definitions can be found in Section 14.1.3.2.8.
 
. =After the last adequate tumor assessment. "Date of next scheduled assessment" is defined in Section 14.1.3.2.8.
 
. =The rare exception to this is if the patient dies no later than the time of the second scheduled assessment as defined in the protocol in which case this is a PFS event at the date of death.
			

The primary analysis and the sensitivity analyses must be specified in the protocol. Clearly define if and why options (1) are not used for situations C, E and (if applicable) F.

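### Duration of response ends only at progression or death from the cancer; censoring responders' other deaths can overstate how long responses last, by an amount the protocol cannot fix

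*Protocol*

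**What the plan says.** Protocol Section 10.7.2.1 defines DOR, among confirmed responders, as the "time from first documented response (PR or CR) to the date of first documented disease progression or death due to underlying cancer". Without such an event, "DOR is censored at the time of the last adequate tumor assessment". On the estimator it says "DOR will be described using the Kaplan-Meier method including the estimated median (in months) with 95% CI".

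The same section ends PFS at the "date of first documented disease progression per RECIST 1.1 or death due to any cause".

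Appendix 1 agrees with the DOR text:
- Section 14.1.3.2.6 ties DOR to time to progression (TTP): "the start date is the date of first documented response (CR or PR) and the end date and censoring is defined the same as that".
- Section 14.1.3.2.3: "TTP is defined as PFS except for death unrelated to underlying cancer".
- Table 14-5, situation G, "Deaths due to reason other than deterioration of 'Study indication": the end date is the last adequate assessment and the outcome is censored, for TTP and DOR only.
- Section 14.1.4.5.6 lists a matching censoring reason, again for TTP and DOR only.

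Section 10.7.2.2 extends the endpoint to Group 5: "DOR, DCR, and PFS for capmatinib monotherapy will be analyzed as secondary efficacy endpoints for Group 5". It refers back for the definition. The section number it gives does not match the current numbering, but 10.7.2.1 is evidently meant.

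**The concern.** A response ends when the responder dies, whatever the cause. Under this definition a responder who dies before progression of, say, a treatment toxicity leaves the DOR risk set as a censored observation, dated to a scan before the death. Kaplan-Meier then assumes that this person's later course would have resembled that of the responders still under observation. Death is a competing event, so that assumption has no sensible meaning here.

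Two further features matter:
- Whether a death counts depends on the recorded reason (Section 14.1.3.2.2 has two categories, the study indication or other). The trial is single-arm and those recording the reason know the treatment. Death from any cause needs no such judgement.
- No control arm carries the same distortion, so the reported median stands alone beside the response rate.

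At stake is the descriptive reading of DOR: a median that may look somewhat longer than responses actually lasted.

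**Working it through.** The protocol gives no assumed DOR, no non-cancer death rate and no precision target for DOR, so there is no stated figure to reproduce. The check has three parts.

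**1. One death, three endpoints.** Take a responder who dies of a non-cancer cause before progression, with scans up to date.

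| Endpoint | Status | Time used |
|---|---|---|
| PFS (10.7.2.1) | event | date of death |
| DOR (10.7.2.1) | censored | last adequate scan |
| DOR (Table 14-5, situation G) | censored | last adequate scan |

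The PFS row assumes fewer than two missing evaluations before the death and no new anticancer therapy; otherwise PFS is censored too.

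**2. Direction.** Under the all-cause definition, a death with m responders at risk multiplies the Kaplan-Meier curve by (m−1)/m. Under the protocol's definition that factor is absent, so from the date of death onward the curve is equal or higher. It is unchanged if no such death occurs. There is one small exception. Because censoring is dated back to the last scan, another responder's event between that scan and the death is taken over a risk set one smaller, so the curve can dip slightly in that short interval before ending higher.

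**3. Size, on assumed inputs.** Let f be the share of response-ending events that are non-cancer deaths. f is not in the document; the range 0–20% is an assumption. With constant hazards and total rate λ, the all-cause median is ln 2/λ. Censoring the share f leaves the rate λ(1−f) and the median ln 2/[λ(1−f)]. The ratio is 1/(1−f).

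| f (assumed) | 1/(1−f) | an assumed 12.0-month median reads as |
|---|---|---|
| 0% | 1.00 | 12.0 |
| 5% | 1.053 | 12.6 |
| 10% | 1.111 | 13.3 |
| 15% | 1.176 | 14.1 |
| 20% | 1.25 | 15.0 |

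A simulation on the same assumptions added 8-weekly scans, censoring at the last scan and 12 to 36 months of follow-up (40,000 responders per scenario).

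| f | 12-month rate, all-cause | 12-month rate, as defined | median, all-cause | median, as defined |
|---|---|---|---|---|
| 5% | 0.527 | 0.545 | 12.88 | 12.88 |
| 10% | 0.526 | 0.563 | 12.88 | 14.72 |
| 20% | 0.523 | 0.598 | 12.88 | 16.56 |

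The simulated medians move in steps of 56/30.4375 = 1.84 months because progression is seen only at scans. That is why nothing shows at 5%; the 12-month rates show the shift more smoothly.

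**What f means in people.** Section 10.5.2.2 needs at least 22 responders of 40 in Group 3. If all 22 responses end, two non-cancer deaths give f = 2/22 = 9% and a ratio of 22/20 = 1.10; four give f = 4/22 = 18% and 22/18 = 1.22. With 11 responders of 20, one of the examples in Table 10-4, one such death gives f = 1/11 = 9% and 11/10 = 1.10.

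**The case against.** The strongest reply is that nothing here is an error. The body text and four places in Appendix 1 state the same rule, and the appendix openly separates the TTP-type endpoints from PFS. Time in response until failure of tumour control is a recognisable target, and the upward shift is a bias only relative to the all-cause target. This stands in part. A reader might infer from the two death definitions that DOR and PFS contradict each other; the documents do not support that, because they are two endpoints with two declared event definitions. But declaring the rule does not make a competing death non-informative, and Table 14-5 allows the protocol to depart from its defaults.

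Other points on that side:
- **Practical effect.** With 22 events, an exponential approximation puts the 95% interval for the median at exp(±1.96/√22), about 0.66 to 1.52 times the estimate. A 5–11% shift is small against that. True, though a shift in one direction is not removed by being smaller than the noise.
- **Consequences.** Success and futility rules use response rate only, and Section 10.11 plans no power for secondary variables. Section 14.1.3.2.6 itself urges caution with responder-only summaries. Non-cancer deaths still count in PFS and, for Groups 1 to 4, in overall survival. All of this stands and limits the weight of the point.
- **Reach.** Phase Ib gets a Kaplan-Meier summary only where numbers suffice, groups with five or fewer responders get summary statistics, and Group 2 has about five participants. The definition applies throughout; the effect on a Kaplan-Meier median will not arise everywhere.
- **Cause of death.** Judgement by those who know the treatment also underlies the investigator-assessed response rate. That is so, but here the judgement is avoidable.
- **Sensitivity analyses.** An all-cause DOR may be planned in the SAP, which is not at hand. Its absence from the protocol is not held against it; the point concerns the main definition only.

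**Conclusion.** The point holds as a cheap improvement. The main DOR definition censors responders who die of a cause other than the cancer, so the reported curve is, from such a death onward, equal to or above the all-cause curve, and it depends on cause-of-death attribution.

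Three stronger readings should be resisted:
- That DOR is always lengthened. With no such deaths nothing changes, and deaths beyond the median leave the median where it is.
- That an inflation of 5% to 25% is to be expected. Those figures rest on assumed shares and constant hazards; the protocol gives no non-cancer death rate and nothing in it supports the upper end.
- That the trial's conclusions are at risk. DOR is a descriptive secondary endpoint; response rate, decision rules and sample sizes do not depend on it.

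**What to change.** In Section 10.7.2.1, define DOR as the time from first documented response to first documented progression or death from any cause. Make the matching change for DOR, leaving TTP as it is, in Section 14.1.3.2.6, Table 14-5 situation G and the censoring reasons in Section 14.1.4.5.6. Group 5 follows through Section 10.7.2.2. The cancer-death version can stay as a sensitivity analysis, and a listing of non-cancer deaths among responders would show the reader how much depends on it.

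The cost is one definition and a small programming change. PFS already requires the same death dates, so no new data are needed. The downsides are a DOR that may look slightly less favourable and a departure from the sponsor's standard TTP-based default.
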